2.3 AKI SAFETY, MORTALITY AND DEVICE INTEGRITY STUDY (CHINA)^[21]

2.3.1 STUDY SUMMARY

Despite decades of improvements in the provision of renal replacement therapy, the morbidity and mortality associated with acute kidney injury (AKI) in the intensive care unit (ICU) setting remains extremely high. Much of the morbidity and mortality of this disorder is the consequence of systemic cellular damage that results from immune dysregulation. This was a prospective, single-arm, single-center study designed to evaluate the safety and efficacy of treatment with a selective cytopheretic device (SCD) on clinical outcomes in AKI requiring renal replacement therapy in the ICU. The patients enrolled in the trial were compared with historical case-matched controls with respect to age and Sequential Organ Failure Assessment (SOFA) score. The mortality for the case-matched controls was 77.78%, whereas the mortality in the SCD treatment group was 22.22% ($p = 0.027$). Multiple regression analysis identified treatment with SCD as the only significant variable affecting mortality among age, SOFA score, and average change in urine output over the first 7 days during or after treatment. Mean total urine output in the 10 subjects receiving SCD treatment increased from a baseline of approximately 500 ml/d to more than 2,000 ml/d by day 7 of treatment.

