2.3.2 SAFETY RESULTS

A total of 12 patients were enrolled in this study. There were no SAEs reported.

In the 9 subjects analyzed on SCD treatment, no neutropenic events were reported. Mean WBC counts remained normal throughout treatment, with a mild decline noted upon initiation of therapy that was shown to rebound by day 7. No bleeding events were reported. Average platelet counts remained in the functional range (above 50,000) throughout treatment, with a mild decline noted upon initiation of therapy that was shown to plateau by day 4 to an average platelet count of 75,000. A summary of all adverse events (AEs) observed in the 9 subjects on SCD treatment is presented in **Table 2**. These events were not attributed to the

device by the investigator, as they commonly occur with CRRT treatment.

Table 2: Adverse event reporting – China Study – n=9 patients

Adverse Event (n=9 patients)	Number of Mild Severity Events	Number of Moderate Severity Events
Hypercalcemia	6	2
Thrombocytopenia	1	0
Hypocalcemia	0	1
Allergic Reaction	1	0
Hypophosphatemia	2	0
Hypernatremia	1	0

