6.5.3 DAY 60 POST ENROLLMENT

This visit may be done via telephone call or office visit. Please record the following information on day 60 (+7 days) following enrollment:

- Presence / dates of mechanical ventilation (since last visit)
- Presence / dates of renal replacement therapy (since last visit)
- ICU discharge date
- Hospital discharge date
- Serious Adverse events (since last visit)
- Serum creatinine (if an office visit takes place)

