APPENDIX D – ENDPOINT DEFINITIONS

ALL-CAUSE MORTALITY:

All cause mortality is defined as in-hospital, 28-day and 60-day all cause mortality.

DIALYSIS DEPENDANCY AT DAY 60:

Dialysis dependency at day 60 is defined as patient not receiving any form of intermittent or continuous renal replacement therapy at or within 3 days of 60 days post enrollment in the study with no plans for additional intermittent or continuous renal replacement therapy.

PATIENT SAFETY:

Adverse events, laboratory safety parameters, vital signs, EKG, ventilation status and hemodynamic variables.

DURATION OF RENAL SUPPORT:

The duration of renal support will be defined as the numbers of days from the initiation of renal replacement therapy (start of observation period) to final dialysis treatment. Duration of renal support will be censored if the patient is still dialysis dependent at the time of death or are dependent at day 60.

RECOVERY OF RENAL FUNCTION:

Recovery of renal function will be defined as lack of need for continuous dialysis support on day 28, and will be classified as yes or no at day 28. Subjects who were alive at day 28 will be included in the analysis. Patients who remain dialysis dependent at study completion (day 60) or time of death will be categorized as having no recovery of renal function.

ASSESSMENT OF SCD █ INTEGRITY AND PERFORMANCE:

The SCD █ will be evaluated for the presence of clotting, leaking or any other malfunction.

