¹Events listed in this column are to be performed once per 24 hour time period.

APPENDIX H – SCD-PED-01 Study Schedule of Events: Day 28 and Day 60

Measurement	Day 28 ¹	Day 60 ²
Presence of mechanical ventilation (since last visit)	X	X
Presence of renal replacement therapy (since last visit)	X	X
Hospital and ICU Discharge information	X	X
Serious Adverse events (since last visit)	X	X
Serum Creatinine (if office visit takes place)	X	X

¹ This visit may be done via telephone call or office visit. Please record the above information on day 28 (+7 days) following enrollment.

² This visit may be done via telephone call or office visit. Please record the above information on day 60 (+7 days) following enrollment.

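### Day-60 dialysis dependency is defined by a window and a no-plans clause that the listed day-60 data do not fully cover, and its wording is inverted

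*Combined protocol and SAP*

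**What the plan says.** Appendix D, under dialysis dependency at day 60, classifies a patient on two limbs: RRT status around day 60 and, for a patient off RRT, whether more is planned. The patient must be off RRT "at or within 3 days of 60 days post enrollment in the study with no plans for additional intermittent or continuous renal replacement therapy". The sentence attaches the label of dependency to the patient who is not receiving RRT.

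The only contact that supplies this endpoint is the day-60 telephone call or office visit. Section 6.5.3 sets its timing: "Please record the following information on day 60 (+7 days) following enrollment". Its RRT item is "Presence / dates of renal replacement therapy (since last visit"; the schedule in Appendix H shortens this to "Presence of renal replacement therapy (since last visit", with no dates. The other items are ventilation, ICU and hospital discharge, serious adverse events (SAEs), and creatinine if there is an office visit. The day-28 contact (Section 6.5.2) may fall on days 28 to 35. The synopsis sets follow-up at 60 days, and no later contact is planned.

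The synopsis evaluation plan rests on safety and on death or dialysis dependency through day 60, with both rates compared with historical controls.

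**The concern.** An endpoint can be scored as defined only if each part of the definition has a data source covering the right days. Here one part, planned RRT, has no listed source. Another, the window around day 60, may extend beyond the day of the contact.

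A child could be last dialysed on day 56, called on day 60, and have a session due on day 61. The recorded dates show no RRT on days 57–60, and nothing listed would reveal the planned session. The child would be scored dialysis-free, although the no-plans clause, and the later days of a two-sided window, would catch exactly this case.

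At stake is a rate that will be set beside a historical rate in a very small cohort, where one child matters. The inverted label adds a separate risk: taken literally, the definition counts dialysis-free children as dependent.

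**Working it through.** **Inputs.** Window: within 3 days of day 60 (Appendix D), direction not stated. Permitted contact days: 60 to 67, which is 8 days (Section 6.5.3, Appendix H). Previous contact: days 28 to 35 (Section 6.5.2). Enrolment: up to 30 (Section 5.1), or 16 as in the monitoring-board plan (Section 10). The plan gives no figure of its own on this point to reproduce.

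**Step 1: window coverage, with RRT dates recorded.** For a contact on day c, the observed days of a 57–63 window are min(c, 63) − 57 + 1, and the unobserved days are max(0, 63 − c).

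| Contact day | Days 57–63 observed | Unobserved | Days 57–60 observed |
|---|---|---|---|
| 60 | 60 − 57 + 1 = 4 of 7 | 3 | 4 of 4 |
| 61 | 5 of 7 | 2 | 4 of 4 |
| 62 | 6 of 7 | 1 | 4 of 4 |
| 63–67 | 7 of 7 | 0 | 4 of 4 |

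On the two-sided reading, 3 of the 8 permitted days fall short and 5 do not. On a backward-only reading (days 57–60), none falls short.

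**Step 2: coverage if only presence is recorded (Appendix H).** The answer refers to the whole interval since the day-28 contact. That is at least 60 − 35 = 25 days and at most 67 − 28 = 39 days. A yes cannot be placed inside the window: a child dialysed on day 40 who then came off would also be a yes. A no given on day 63 or later still shows that there was no RRT in the window.

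**Step 3: the no-plans limb.** A child with RRT inside the window can be classified without it. A child with none needs it. No listed item supplies it on any of the 8 contact days, and past dates do not show intent.

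**Step 4: weight of one child.** Assume 35% mortality, from the 65% survival that Section 11 cites for registry patients on CRRT for 1 to 7 days.

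- At 30 enrolled: 30 × 0.65 = 19.5 survivors. One child is 1/19.5, about 5 points of dependency among survivors, and 1/30 = 3.3 points of the composite.
- At 16 enrolled: 16 × 0.65 = 10.4 survivors. One child is 1/10.4, about 10 points, and 1/16 = 6.3 points of the composite.

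With the 10–20% non-recovery in Section 1.1, the expected number of dependent children is 2.0 to 3.9 of 19.5, or 1.0 to 2.1 of 10.4. In the US pilot study (Section 2.4.1) all survivors were dialysis-independent at day 60, so the range should reach down to zero.

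**The case against.** The strongest reply is that most of this can be scored. Section 6.5.3 asks for dates, so RRT can be placed relative to day 60 whenever the call is made, and a day-67 call does not yield a status seven days late. Appendix H is a short schedule table that also drops the ventilation dates, so its omission may be only abbreviation. Sixty days of follow-up fits a backward window, for which every permitted contact suffices. The case report form is not in the documents, and the text between Appendices H and J is not included either; a planned-RRT field may exist. The trial is not powered (Section 11), and nothing shows that a misclassification will occur.

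Much of that stands. It confines the timing gap to contacts on days 60–62 under a two-sided reading, and the day-40 example to use of Appendix H. It does not supply the planned-RRT item, settle the window, or reconcile Section 6.5.3 with Appendix H.

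A reader might also infer that deaths will be lost, because vital status is not a listed item at either contact and the China study summary says "There were no SAEs reported" although "the mortality in the SCD treatment group was 22.22" percent. The documents do not support that. Here death is an SAE (Section 9.2), SAEs are recorded to day 60 and reported within 24 hours of knowledge (Section 9.7.2), both contacts ask for them, and death is a listed reason for ending therapy (Section 7.3). The China study's SAE definition is not given. In the US pilot the adverse-event table shows 11 deaths, and 11/35 = 31.4%, the day-60 mortality reported. What remains is that no listed item positively records that a child is alive, or when last known alive.

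**Conclusion.** The point holds as a gap between a definition and the data listed for it. Planned RRT has no listed source on any reading of the window. Part of the window is unseen only if it runs to day 63 and the contact falls on day 60, 61 or 62. RRT cannot be dated only if Appendix H governs. The inversion is a plain drafting error.

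A reader might conclude that the endpoint cannot be scored at all. That goes too far: with the Section 6.5.3 dates, days 57–60 can be scored from any permitted contact, and days 57–63 from contacts on days 63–67.

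The size is stated per child, about 5 points of dependency among survivors at 30 enrolled and 10 at 16. It rests on the assumed 35% mortality, taken from a registry subset. It says how much one error would matter, not how likely one is; the documents give no basis for a frequency. The change is worth making because it is cheap and the rate will be compared with historical controls.

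**What to change.** 1. Rewrite the Appendix D definition so that dependency means dependency. The present sentence describes independence: no RRT in the window and none planned.
2. State whether the window is days 57–63 or days 57–60. If 57–63, make the day-60 contact on days 63–67, inside the existing allowance. If 57–60, the timing can stay as it is.
3. At the day-60 contact record the date of the last RRT session, any RRT in the window (yes/no), and further RRT planned (yes/no).
4. Align Appendix H with Section 6.5 on dates.
5. At both the day-28 and day-60 contacts record vital status, with date of death or date last known alive.

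The cost is a few data fields and an edit to two appendices and Section 6.5. No visit is added and treatment is unchanged. The one downside, under the 57–63 window, is that sites lose days 60–62 for making the call.

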5.3 EXCLUSION CRITERIA

1. Threshold blood pressure of 80/40 mmHg-- patients with both a systolic blood pressure of less than 80 mmHg and a diastolic blood pressure of less than 40 mmHg.
2. Irreversible brain damage based on available historical and clinical information.
3. Patients with a solid organ transplant or those with a bone marrow or stem cell transplant in the previous 100 days or who have not engrafted.
4. Acute or chronic use of circulatory support device, other than ECMO, such as LVADs, RVADs, BIVADs.
5. Presence of preexisting advanced chronic renal failure (i.e., ESRD) requiring chronic renal replacement therapy prior to this episode of acute kidney injury or with pre-existing chronic kidney disease (CKD) defined as a eGFR <30 ml/min/1.73m 2 . Patients who have never seen a pediatric nephrologist will be assumed not to have pre-existing CKD.
6. AKI occurring in the setting of burns, obstructive uropathy, vasculitis, scleroderma renal crisis, atheroembolism, functional or surgical nephrectomy, cyclosporine or tacrolimus nephrotoxicity.
7. Received >12 hour of CRRT (not including SCUF on ECMO) during this hospital admission or prior to transfer from an outside hospital.
8. Received >1 hemodialysis treatment during this hospital admission or prior to transfer from an outside hospital.
9. Metastatic malignancy which is actively being treated or may be treated by chemotherapy or radiation during the subsequent three month period after study therapy.
10. Chronic immunosuppression with the exception of corticosteroids up to a dose of 10 mg per day.
11. HIV or AIDS.
12. Severe chronic liver failure as determined by standard diagnostic requirements.

13. Current Do not Attempt Resuscitation (DNAR), Allow Natural Death (AND), or withdrawal of care status, or anticipated change in status within the next 7 days.
14. Patient not expected to survive 28 days because of an irreversible medical condition. (This is not restrictive to AKI, and may include situations such as the presence of irreversible brain damage, untreatable malignancy, inoperable life threatening condition, or any condition to which therapy is regarded as futile by the PI.)
15. Any medical condition that the Investigator thinks may interfere with the study objectives.
16. Physician refusal.
17. Dry weight <15 kg.
18. Platelet count <15,000/mm³.

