6.4 STUDY OBSERVATION PERIOD

The Study Observation Period begins when the patient starts treatment and will continue up to a maximum of 168 hours from the time of Observation Start. **Patient will begin the Observation Period before the patient has reached 12 hours on CRRT.** A patient may begin CRRT therapy and SCD treatment at the same time, which would also mark the beginning of the Study Observation Period.

This observation period has been broken into seven 24 hour time periods. It ends when the patient has reached 168 hours in the observation period or when the patient meets the termination criteria outlined in **Section 7.2** as determined by the Principal Investigator or Medical Team at the participating Clinical Site.

All tests are scheduled on a 24 hour cycle, or once a day, and can be scheduled to be drawn around each participating site's ICU blood drawing schedule, with the exception of any test that requires a specific draw frequency.

The following information will be obtained for patients enrolled during the study observation period on a daily basis unless otherwise specified:

- **Vital Signs/Physical Assessment**
 - Temperature
 - Blood Pressure , heart rate
 - Urine Output (previous 24 hours)
 - Net Fluid Balance (previous 24 hours)
- **Clinical Laboratory Tests**
 - CBC with differential – every 12 hours (+/- 4 hours)
 - BUN, Creatinine
 - Na, K, Cl, HCO₃, Ca, ionized Ca, Mg, PO₄
 - ALT, AST, Bilirubin, ALP, Total Protein, Albumin, Glucose
 - PT, PTT, INR
- **Respiratory**
 - Status – Ventilator support (yes/no; date of extubation)
 - If on Vent: FiO₂
 - If on Vent with an arterial line: Arterial Blood Gas
 - If on Vent without an arterial line: Arterial Blood Gas (if available)
- **Blood for Research**
 - Collect at hours 48, 96, 144, and end of study (+/- 4 hours). If study observation period ends prior to hour 168, collect at end of study observation period. Blood for biomarkers will be collected as close as possible to the time of SCD scheduled changes in the days required (+/- 4 hours) if practical.
 - Blood sample will be sent to an outside laboratory for testing of biomarkers

- **CRRT Parameters (Start at hour 0)**
 - Parameters include modality, blood flow rate, net fluid removal, dialysate or replacement solution flow rate, citrate infusion rate, calcium replacement rate.
 - System performance (circuit survival - event driven)
 - Post filter ionized calcium (+/- 1 hour)

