The Prospective Pediatric CRRT (ppCRRT) database will be used as a control for the CRRT treatment related factors including: patient age, gender, primary cause of AKI, total treatment duration, CRRT modality (CVVH, CVVHD, CVVHDF), CRRT small solute clearance (ml/1.73m²/hour), baseline estimated GFR (using the original Schwartz formula, which was used in the ppCRRT), urine output in the 24 hours prior to CRRT initiation (ml/kg/hour), percent fluid overload at CRRT initiation based on admission ICU weight, vasoactive medication number at time of CRRT initiation and mean airway pressure at CRRT initiation.

An additional analysis will also evaluate patients who have achieved targeted iCa levels during 90% of treatment time and those who do not.

In summary this protocol meets all criteria necessary for clinical scientific inquiry related to a test of hypothesis in a well monitored environment focused on patient safety during the conduct of the study. Basic statistics will be performed on the data sets along with historical data comparisons and subjected to subset analysis where appropriate. The results will help to guide the design of a future pivotal study of this device.

The rational for therapy, study objectives and endpoints, design, inclusion and exclusion criteria are explicitly defined. Patient safety parameters are well documented including safety reporting, safety observations and assays, procedures for patient withdrawal and study discontinuation criteria along with monitoring device integrity and performance. Lastly, a review of all prior SCD human study safety data is included in the protocol for full disclosure to study investigators and the informed consent document includes a full description of all known and potential risks of the device treatment.

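### Appendix D censors duration of renal support at death on dialysis, which under an ordinary censored analysis overstates dialysis discontinuation; its clock can also start up to 12 hours after CRRT began

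*Combined protocol and SAP*

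**What the plan says.** **Duration of renal support (Appendix D).** The clock counts "the numbers of days from the initiation of renal replacement therapy (start of observation period) to final dialysis treatment". On deaths, "Duration of renal support will be censored if the patient is still dialysis dependent at the time of death"; patients still dependent at day 60 are censored too. No estimator is given there, and Section 11 promises only basic statistics and comparisons with historical data.

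**Recovery of renal function (Appendix D, next entry).** This is a yes/no outcome at day 28. It analyses only subjects alive at day 28, yet it also scores anyone dialysis dependent at death, or at day 60, as not recovered.

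**Time to renal recovery (Section 3.2).** It is listed as a clinical efficacy measure. Appendix D gives it no time-to-event definition, so the duration entry is the nearest one available.

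**What may precede the observation period.** Section 6.4 states "Patient will begin the Observation Period before the patient has reached 12 hours on CRRT", and also "A patient may begin CRRT therapy and SCD treatment at the same time". Section 5.3 excludes a child only if the child "Received >12 hour of CRRT (not including SCUF on ECMO) during this hospital admission" (item 7) or "Received >1 hemodialysis treatment during this hospital admission or prior to transfer from an outside hospital" (item 8). One earlier haemodialysis session is therefore allowed, with no limit on how long before.

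**Registry and analysis set (Section 11).** Several registry factors are fixed at the start of CRRT, for example "vasoactive medication number at time of CRRT initiation". Total treatment duration is on the same list. Entry to the final outcome analysis requires at least 72 hours of SCD treatment.

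**The concern.** Censoring assumes that a patient who leaves observation had the same prospects as those who remain. A child who has died on dialysis will never come off it. Under ordinary censoring, that child's probability is passed on to the survivors still at risk. The curve then describes dialysis discontinuation as if nobody died, and a group with more deaths on dialysis shows no penalty for them. Section 11 hypothesises that SCD may shorten dialysis, and the pilot is meant to guide a pivotal design, so an inflated curve could carry forward into planning.

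The recovery entry adds to the difficulty. A child who dies on dialysis before day 28 is censored in one entry, classed as not recovered in the next, and left out of that entry's analysis set.

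The clock is the lesser issue. The definition treats the start of RRT and the start of observation as one event, although the protocol lets CRRT come first. Any resulting error can only shorten the recorded duration.

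**Working it through.** The documents give no sample size, power or expected duration for this endpoint, so there is no stated figure to reproduce.

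**Step 1. Size of the censoring effect**

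Inputs:
- Deaths, D: 31.4% (adult US pilot, Section 2.4.1); 35%, being 100% − 65% survival among registry patients with 1–7 days of CRRT (Section 11); 50% (upper figure, Section 1.1); and 20% as an assumed low value.
- Still dependent at day 60, P: 10% and 20%, from the 10–20% non-recovery in Section 1.1, applied here to all patients.
- Recovered by day 60: R = 1 − D − P.

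Assumptions: constant rates over 60 days, and every death on RRT.

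Formulas:
- Total rate = −ln(P)/60.
- Recovery rate = total rate × R/(R + D).
- Apparent recovery with deaths censored = 1 − exp(−60 × recovery rate) = 1 − P^(R/(R+D)).
- Actual cumulative incidence of recovery by day 60 = R.

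Example with D = 35%, P = 10%, so R = 55%:
- Total rate = 2.3026/60 = 0.03838 per day.
- Recovery rate = 0.03838 × 0.55/0.90 = 0.02345 per day.
- Apparent recovery = 1 − exp(−1.407) = 75.5%, against an actual 55.0%.
- Apparent median = 0.6931/0.02345 = 29.6 days. The day by which half of all patients have actually come off dialysis is −ln(1 − 0.5 × 0.90/0.55)/0.03838 = 44.4 days.

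| Deaths D | Dependent P | Actual R | Apparent, deaths censored | Gap (points) |
|---|---|---|---|---|
| 20% | 10% | 70.0% | 83.3% | 13.3 |
| 20% | 20% | 60.0% | 70.1% | 10.1 |
| 31.4% | 10% | 58.6% | 77.7% | 19.1 |
| 31.4% | 20% | 48.6% | 62.4% | 13.8 |
| 35% | 10% | 55.0% | 75.5% | 20.5 |
| 35% | 20% | 45.0% | 59.6% | 14.6 |
| 50% | 10% | 40.0% | 64.1% | 24.1 |
| 50% | 20% | 30.0% | 45.3% | 15.3 |

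With no deaths on RRT, R/(R + D) = 1 and the apparent value is 1 − P = R, so the gap is zero.

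**Step 2. Size of the clock effect**

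- Offset from CRRT: 0 if CRRT and SCD start together, otherwise under 12 hours (0.5 day).
- For a patient who meets the 72-hour rule, the largest share of the course is 12/(72 + 12) = 14.3%.
- For longer courses: 0.5/7 = 7.1% of 7 days and 0.5/28 = 1.8% of 28 days.
- An earlier haemodialysis session would add an interval that the documents do not bound.
- The offset affects recorded length, not the share of patients who come off dialysis.

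**Step 3. The two Appendix D entries side by side**

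| Patient | Duration entry | Recovery entry |
|---|---|---|
| Dies on dialysis before day 28 | Censored at death | Classed as not recovered, but outside the analysis set |
| Dies on dialysis between days 28 and 60 | Censored at death | In the analysis set, not recovered |

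The two entries do not treat death on dialysis consistently, and the recovery entry's scoring rule reaches patients whom its own analysis set leaves out.

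**The case against.** **No estimator is named.** This is correct. The overstatement follows from the ordinary meaning of censoring, not from a stated method, so it must be put conditionally. An analyst could still choose a competing-risk method, but nothing in the plan says so.

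**Deaths are counted elsewhere.** All-cause mortality is the primary efficacy measure, and the synopsis evaluates mortality or dialysis dependency through day 60. A reader of the full report would see the deaths. The duration curve would still mislead if read by itself.

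**A much larger gap might be inferred.** With a total rate of 0.10 per day and 35% or 50% dying on dialysis, censoring would show 98% or 95% off dialysis against a true 65% or 50%. Those rates leave only exp(−6) = 0.25% of patients dependent at day 60, against the protocol's 10–20% non-recovery. The adult US pilot does report every survivor dialysis independent at day 60, so a lower dependent share is possible, but it does not say how many deaths occurred on dialysis. The mortality figures used here are deaths from any cause, so placing them all on RRT is an upper bound.

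**A reader might infer that trial durations are always shorter than registry durations, by up to half of a one-day course.** The documents do not support this. A simultaneous start is allowed, so the offset may be zero. A one-day course cannot meet the 72-hour rule, if that rule covers this endpoint. No registry comparison of duration is stated: the historical comparison names mortality and dialysis dependency, and total treatment duration appears only as a control factor.

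**An earlier origin has its own cost.** Starting at CRRT initiation adds time that trial patients had to survive in order to enrol. This stands, but it covers less than 12 hours and can be handled in the analysis. Starting at an earlier haemodialysis session would be worse, because the gap is unbounded and could count RRT-free days as renal support.

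**This is an unpowered pilot of up to 30 patients.** True, and it limits the consequence. It is not a reason to leave the definition as it is.

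**Conclusion.** The point holds in a limited form. Appendix D censors death on dialysis. Under ordinary censoring this overstates dialysis discontinuation by about 10 to 24 percentage points, given constant rates, all deaths on RRT, 20–50% deaths and 10–20% still dependent at day 60. The true effect may be smaller, and it vanishes if few children die on RRT. It concerns the duration or time-to-recovery curve, not the yes/no recovery outcome, whose own two rules need reconciling.

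The clock is a secondary defect: 0 to under 0.5 day of CRRT, or at most about 14% of the course for patients meeting the 72-hour rule. It would put trial and registry on different origins only if durations are compared.

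**What to change.** - **Death.** Report time to dialysis discontinuation as cumulative incidence through day 60, with death on RRT as a competing event. Censor only patients alive and still on RRT at day 60 or last contact.
- **Clock.** Start at actual CRRT initiation and remove the parenthesis that equates it with the start of observation. Use the same origin for any registry comparison, with trial patients entering the risk set at observation start. Record any earlier haemodialysis session separately.
- **Recovery entry.** State whether patients who die on dialysis before day 28 count as not recovered or are left out, and make the two sentences agree.
- **Optional supplement.** Days alive and free of RRT to day 60.

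The cost is small: revised Appendix D wording and slightly different analysis code. The time of CRRT initiation is already needed for the fluid-overload item in Section 6.3 and for exclusion 7, and RRT dates are collected at days 28 and 60 (Sections 6.5.2 and 6.5.3). Reported durations become slightly longer and the curve less favourable.
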